10.0 Overall Type-I Error Control

The primary comparison for the co-primary will be made between elagolix plus E2/NETA and placebo. The elagolix alone arm will be served as a reference arm. Therefore, no adjustment of the type I error rate (alpha) for the primary endpoint is needed. Ranked secondary endpoints will be tested following a fixed-sequence testing procedure. Specifically, testing will begin with testing each of the co-primary endpoints using alpha of 0.05 (2-sided) for elagolix plus E2/NETA compared to placebo. If both co-primary endpoints achieve statistical significance with elagolix W2/NETA as compared to placebo, continued testing will be performed for the ranked secondary endpoints following a fixed-sequence testing procedure.

11.0 Version History

Table 3. SAP Version History Summary

Version	Date	Summary
1.0	29 April 2020	Original version

12.0 References

Appendix A. Receiver Operating Characteristics (ROC) Analysis for Determination of Thresholds for Reduction in Pain

The ROC analysis will be conducted prior to blind break and will contain all randomized subjects who received at least one dose of study drug. Subjects who prematurely discontinue at or before Month 6 will have their pain scores and PGIC response carried forward (LOCF) – from the previous time point when both PGIC and pain score data are observed. Subjects who a) prematurely discontinue at or before Month 6 and have no month with both a PGIC and e-Diary data (DYS, NMPP, or dyspareunia) to carry forward, or b) either prematurely discontinue after Month 6 or complete the Treatment Period but are missing Month 6 PGIC will be assigned a PGIC response of "No Change." Subjects who a) prematurely discontinue at or before Month 6 and have no month with both a PGIC and e-Diary data (DYS, NMPP, or dyspareunia) to carry forward, or b) either prematurely discontinue after Month 6 or complete the Treatment Period but are missing Month 6 pain scores will be assigned a change from baseline in pain score equal to 0.

The threshold for reduction in pain will be determined based on a ROC analysis using the PGIC assessment at Month 6 as an anchor and change from baseline in pain score (DYS, NMPP, or dyspareunia) at Month 6 as the independent variable. The PGIC is a 7-point response scale "Since I started taking the study medication, my endometriosis related pain has: very much improved (1), much improved (2), minimally improved (3), no change (4), minimally worse (5), much worse (6), very much worse (7)." The responses of "much improved" and "very much improved" on PGIC will be used to define responders, and the threshold for response (the value of X) will be chosen to balance sensitivity and specificity. That is, it is the value that corresponds to the point on the ROC curve that is closest to the upper left corner, i.e., closest to 100% sensitivity and 100% specificity. No other covariates will be included in the ROC analysis.

The ROC analyses for DHS, NMPP, and dyspareunia will be conducted separately. The threshold obtained from the ROC analysis using PGIC at Month 6 and change from baseline to Month 6 in DHS will be fixed and used for all responder analyses at all time

points during the 12-month placebo-controlled Treatment Period. Same applies to NMPP and dyspareunia.

The results of the ROC analyses can be found in [Appendix C](#).

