balance sensitivity and specificity. That is, it will be the value that corresponds to the point on the ROC curve that is closest to the upper left corner when plotting 1-specificity versus sensitivity, i.e., closest to 100% sensitivity and 100% specificity. No other covariates will be included in the ROC analysis. All available subjects will be included in the ROC analysis. For subjects who prematurely discontinue before Month 6, the last available observation prior to discontinuation (Last Observation Carried Forward) will be used in the ROC analysis.

The ROC analysis may identify different response thresholds for DYS and NMPP. The results of the ROC analysis, containing the determined threshold, will be included in the final Statistical Analysis Plan prior to blind break.

The primary analysis of the co-primary endpoint will be based on a logistic regression model including treatment as the main factor and baseline pain score as a covariate to compare the elagolix plus E2/NETA dose group to placebo. For subjects who prematurely discontinue before or at Month 6 of the placebo-controlled Period, last observation carried forward (LOCF) will be used in the primary responder analysis.

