8.1.6.3.2 Dyspareunia

For dyspareunia, responses of "None," "Mild," "Moderate," and "Severe" will be assigned a score of 0, 1, 2, and 3, respectively. The dyspareunia monthly mean scores will be calculated as described above for DYS and NMPP. Responses of "Not applicable" will be excluded from the calculation. If a subject's mean score is not defined because all reports in that month are "Not applicable," then that mean score will be treated as a missing value and will not be included in analyses.

The proportion of responders at each post-baseline Months 1-12 visit will be compared between the elagolix plus E2/NETA dosing group and the placebo group. The threshold for defining responders will be determined using the same ROC method described for DYS and NMPP.

The mean change from baseline to each visit during the first 12 months of the Treatment Period in dyspareunia will be summarized similar to the method for DYS and NMPP. Monthly mean scores will be the average of the daily values reported during the 35 calendar days prior to and including the reference study day as defined in the SAP for the specific time point.

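### The ROC analysis that sets the responder thresholds fills missing data with zero change and 'No Change'; for dyspareunia this conflicts with the protocol, and the effect on all three cut-offs is unreported

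*SAP*

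**What the plan says.** Protocol 8.1.6.1.1 wants X to represent a clinically meaningful reduction in pain. It says "All available subjects will be included in the ROC analysis", and for women who discontinue before Month 6 "the last available observation prior to discontinuation (Last Observation Carried Forward) will be used in the ROC analysis". It gives no rule for a woman with nothing to carry forward, or for one still in the study whose Month 6 value is missing. Protocol 8.1 leaves full detail to the SAP.

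SAP Appendix A says the ROC analysis "will contain all randomized subjects who received at least one dose of study drug". Its rules are:

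- Discontinued at or before Month 6, with a usable month: PGIC and pain score are carried forward as a pair, "from the previous time point when both PGIC and pain score data are observed".
- Discontinued at or before Month 6, with no month holding both: PGIC is set to 'No Change' and pain change to 0.
- Completed, or discontinued later: those who "are missing Month 6 PGIC will be assigned a PGIC response of" 'No Change', and those "missing Month 6 pain scores will be assigned a change from baseline in pain score equal to 0".

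The rules apply to DYS, NMPP and dyspareunia alike. Appendix C gives cut-offs of -0.92, -0.55 and -0.30, used at all of Months 1 to 12.

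For dyspareunia, Protocol 8.1.6.3.2 addresses a month in which every report is 'Not applicable': "then that mean score will be treated as a missing value and will not be included in analyses". The same section says the dyspareunia threshold is to come from the same ROC method.

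**The concern.** A cut-off anchored on PGIC should reflect how women's observed pain change relates to their observed impression of change. The constants create pairs that no woman reported. A woman who says she is very much improved but has no Month 6 score enters as an anchor responder with zero change. A woman with a large fall in pain but no PGIC enters as an anchor non-responder.

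Dyspareunia is the most exposed. 'Not applicable' is the prescribed answer for women not sexually active for reasons other than endometriosis (Protocol 5.3.1.1), so missingness there is structural. Such a woman still gives a real PGIC on her overall endometriosis pain, and Appendix A pairs it with an invented zero.

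The responder analysis itself does not use these constants. SAP 8.2 and 8.3.2 carry values forward only after premature discontinuation and assign nothing to a completer who lacks Month 6 data. The cut-off therefore rests partly on data that the endpoint analysis does not contain. None of the six sensitivity analyses in SAP 8.3.4 varies X, and the Appendix C table does not say how many women were imputed.

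At stake are the description of X as clinically meaningful and the absolute responder rates.

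**Working it through.** **What can be reproduced.** The Appendix C cut-offs cannot be: the documents give no subject data, no missing-data counts and no ROC coordinates. The plan's power statement can. For NMPP, 35% of 200 against 54% of 400, two-sided 0.05:

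- Pooled rate = (70 + 216)/600 = 0.477; null SE = sqrt(0.477 × 0.523 × (1/200 + 1/400)) = 0.0433.
- Alternative SE = sqrt(0.35 × 0.65/200 + 0.54 × 0.46/400) = 0.0419.
- Power = Φ((0.19 - 1.96 × 0.0433)/0.0419) = Φ(2.51) = 99.4%. For DYS it exceeds 99.9%.

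This agrees with the stated figure of more than 90%.

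**Model for the direction and size of the shift.** Let π be the share of PGIC responders, and Fp(c) and Fn(c) the shares of anchor responders and non-responders with change at or below c. The SAP picks c to minimise (1 - Se)² + (1 - Sp)². With missingness independent of outcome:

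- *Both missing, share b:* Se = Fp, unchanged; 1 - Sp = Fn × (1-b)(1-π)/[(1-b)(1-π) + b]. Certain true negatives are added, so c moves toward zero.
- *Pain only missing, share a:* Se = (1-a)Fp and 1 - Sp = (1-a)Fn. Sensitivity is capped at 1 - a, so c moves toward zero.
- *PGIC only missing, share g:* Se = Fp; 1 - Sp = [(1-g)(1-π)Fn + g(πFp + (1-π)Fn)]/[(1-g)(1-π) + g]. Real improvements are counted as false positives, so c moves away from zero.

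**Assumed inputs** (mean, SD of change; not from the documents, chosen so that the cut-off without constants lies near Appendix C):

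- DYS: responders -1.45, 0.75; non-responders -0.40, 0.70.
- NMPP: -0.95, 0.60; and -0.20, 0.50.
- Dyspareunia: -0.75, 0.70; and 0, 0.50.
- π = 35% or 50%.

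**Results.** Shift in cut-off; plus means toward zero; ranges span the two values of π.

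| Share imputed | DYS | NMPP | Dyspareunia |
|---|---|---|---|
| None (cut-off) | -0.92 | -0.57 | -0.36 |
| Both, 5% | +0.03 to +0.04 | +0.02 to +0.03 | +0.02 to +0.03 |
| Both, 10% | +0.06 to +0.07 | +0.04 to +0.06 | +0.05 to +0.06 |
| Pain only, 5% | +0.04 | +0.03 | +0.03 |
| Pain only, 10% | +0.08 | +0.05 | +0.05 |
| Pain only, 30% | – | – | +0.18 |
| PGIC only, 5% | -0.01 to -0.02 | -0.01 | -0.01 |
| PGIC only, 10% | -0.02 to -0.04 | -0.01 to -0.03 | -0.01 to -0.03 |
| 3% both, 2% pain only, 10% PGIC only | 0.00 to +0.01 | 0.00 to +0.01 | 0.00 to +0.01 |

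The 30% row is shown only for dyspareunia, where structural missingness makes such a share conceivable.

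**What the dyspareunia shift does to response on pain alone.** The share meeting the cut-off among women with observed scores is πFp + (1-π)Fn.

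- At -0.36: Fp = 0.709, Fn = 0.233, giving 40% (π = 35%) or 47% (π = 50%).
- At -0.19, after 30% zero change: Fp = 0.789, Fn = 0.354, giving 51% or 57%.

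That is a rise of 10 to 11 percentage points. The same sum for 5% pain-only missing gives 1.6 points for DYS (41.5% to 43.1%) and for NMPP (40.9% to 42.5%) at π = 35%.

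**Second model.** A simulation with other assumed distributions (200 samples of 700, anchor correlation 0.45 for dyspareunia) moved the dyspareunia cut-off from 0.47 to 0.30 in absolute size at 30% zero change. That is a shift of 0.17, and the share beyond the cut-off rose from 47% to 61%.

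**The case against.** The other side has a good deal to say, and most of it stands for the co-primary endpoints.

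- *A reader might infer that the SAP contradicts the protocol throughout.* The documents do not support that for DYS and NMPP. The SAP keeps the protocol's carry-forward rule and adds rules where the protocol is silent, and Protocol 8.1 delegates detail. It would be a departure only if 'available' means having observed or carried-forward data, and the text does not settle this. For dyspareunia the conflict with 8.1.6.3.2 is real.
- *A reader might infer that the cut-offs have been pulled toward zero.* The PGIC-only rule works the other way, and without counts the net sign is unknown.
- *Few women are likely to be affected for DYS and NMPP.* PGIC is collected monthly to Month 6. The pain score uses 35 days of diary entries, and reporting only the other pain type gives a score of 0, not a missing value (SAP 8.3.1). A woman still in the study receives zero change essentially only with no usable diary pain entry in the window. At 5% imputed, the shift of about 0.03 is below the cut-off's own sampling SD, about 0.05 to 0.07 in simulations on assumed distributions.
- *Dyspareunia response carries less weight.* It is an additional endpoint without multiplicity control; the ranked dyspareunia endpoints are mean changes by MMRM and use no threshold. This limits the consequence but does not remove the conflict.
- *Partial safeguards exist.* The observed-case cumulative distribution plots in SAP 8.5.1 show pain-only response at any cut-off, and DYS and NMPP mean changes are ranked secondaries 1 to 6. Neither shows the composite responder result at another X.
- *Replacing the thresholds is no small step.* Appendix C is already filled in, and Protocol Amendment 7 says all subjects are past Month 36, whereas the primary analysis follows the last Month 12 visit. New co-primary cut-offs now would redefine the endpoints. This is right and shapes the fix.

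**Conclusion.** The point holds in limited form. Appendix A assigns constants that the protocol does not provide for. For dyspareunia they conflict with the protocol's handling of all-'Not applicable' months; for DYS and NMPP the protocol is silent or ambiguous. The likely shift is small for DYS and NMPP (about 0.04 or less per rule at 5% imputed). It could be material for dyspareunia: 0.17 to 0.18 if 30% receive zero change, against a published cut-off of 0.30 in absolute size. All sizes rest on assumed distributions, assumed missing-data shares and missingness unrelated to outcome; the true shares are not in the documents.

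A reader might go further and conclude that the co-primary test is compromised. It is not: the ROC analysis is run before blind break on all arms together, and the same cut-off applies to each arm, so type I error is not in question. What is weakened is the claim that X marks a clinically meaningful reduction, and hence the reading of the absolute responder rates.

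**What to change.** 1. Exclude women whose dyspareunia window holds only 'Not applicable' answers from the dyspareunia ROC, so that Appendix A agrees with Protocol 8.1.6.3.2.
2. Report, for each pain variable, the number of women imputed under each rule: both missing, pain only, PGIC only.
3. Rerun the ROC on observed plus paired carried-forward data, with no assigned constants.
4. Report the responder analyses at the re-derived cut-offs as a sensitivity analysis. If the Appendix C thresholds are already frozen, keep the DYS and NMPP values for the primary test.
5. State in Appendix A how the protocol's reference to available subjects is being read.

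This uses existing data and leaves the primary test unchanged. The cost is a little extra analysis, and the re-derived cut-offs may turn out stricter or more lenient.

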Appendix B. Definition of Adverse Events of Special Interest (AESI)

Adverse Events of Special Interest (AESI) will be identified using the following search criteria:

Item of Safety Interest	Method of Surveillance
Hot flashes	Non-bone related hypoestrogenic effects CMQ
Bone mineral density loss	Osteoporosis/Osteopenia SMQ
Anemia	Cases are identified through the Non-Hemolytic and Non-Aplastic Anemias CMQ Haematopoietic erythropenia SMQ
Bone Fractures	Osteoporosis/Osteopenia SMQ
Rash and hypersensitivity reactions	Anaphylactic reaction SMQ Severe cutaneous adverse reactions SMQ Drug induced rash CMQ
Lipid abnormalities	Dyslipidemia SMQ
Uterine bleeding change	Female reproductive bleeds CMQ
Endometrial safety	Uterine and fallopian tube neoplasms, malignant and unspecified SMQ Reproductive Premalignant Disorders SMQ
Hypoestrogenic AEs (excluding hot flashes, BMD loss, and fractures)	Non-bone related hypoestrogenic effects CMQ
Spontaneous abortion	Termination of pregnancy and risk of abortion SMQ
Obstetrical complications (maternal and infant)	Pregnancy, labor, and delivery complications and risk factors (excluding abortions and stillbirths) SMQ
Psychiatric events	Depression and suicide/self-injury SMQ
Cardiovascular events	Cardiac arrhythmias SMQ, Cardiomyopathy SMQ, and Ischemic heart disease SMQ
Thromboembolic events	Embolic and thrombotic events SMQ
Elevated hepatic transaminases	Drug related hepatic disorders – comprehensive search SMQ Enhanced pharmacovigilance hepatic terms (elagolix product specific) PMQ

[figure not shown]

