DXA scans are required to be performed for all subjects during the Treatment Period at Months 6, 12, 18, 24, 30, 36, 42, and 48 and will be submitted to the central reader for review and analysis. The central reader will be blinded to the subjects' treatment assignment, but not to the corresponding time point.

The window for performing DXA scans at Treatment Months 6, 12, 18, 24, 30, 36, 42, and 48 is \pm 15 days around the respective study visit.

If the results of any post-baseline DXA prior to Month 48, as read by the central reader selected for the study, document either of the following results, the subject must be discontinued from study drug dosing and will enter the Follow-Up Period:

- a Z-score (for subjects < 40 years of age at the time of the Screening DXA) or T-score (for subjects ≥ 40 years of age at the time of the Screening DXA) of < -2.5 in the lumbar spine, total hip or femoral neck OR
- a BMD decrease from baseline of > 8% in the lumbar spine, total hip or femoral neck

If the BMD percent change from baseline of any post-baseline DXA prior to Month 48 cannot be provided by the central reader (i.e., due to scanner changes), then the TA MD must be consulted to confirm if the subject can continue study drug dosing. A BMD decrease at any anatomic region (lumbar spine, total hip **or** femoral neck) that results in discontinuation from the study should be reported as an adverse event (Section 6.1.1).

DXA Scans Performed for Subjects who Prematurely Discontinue in the Treatment Period

DXA scans are required to be performed as part of the Premature Discontinuation visit as follows:

- Subjects who discontinue prior to the Treatment Month 6 visit only if the reason for premature discontinuation is due to the occurrence of a fracture or any newly diagnosed bone condition
- Subjects who discontinue any time at the time of or after the Treatment Month 6 visit, or if one was not performed within approximately 6 months of the PD visit.

However, if a subject is being discontinued from the study due to a Z-score or T-score of < -2.5 in any region, BMD decrease from baseline of > 8% in any region, or TA MD

assessment, additional DXA scans do not need to be performed as a part of the Premature Discontinuation visit procedures. In these circumstances, the subject would enter the Follow-Up Period and continue with required BMD evaluations.

DXA Scans Performed in the Follow-Up Period

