6.1.1.3 Adverse Events of Special Interest

Some adverse events, such as SAEs and adverse events of special interest (AESI), may require additional information to be collected, including family history. AESIs include, but are not limited to rash/hypersensitivity, fracture, neuro-psychiatric (depression, mood swings, etc.) and vasomotor symptoms (hot flush, night sweats).

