9.2.6 Adverse Events of Special Interest

Adverse events of special interest will be summarized by SOC and PT and will be based on standardized or company MedDRA queries (SMQs or CMQs), or based on adjudication results.

Detailed information about the search criteria are provided in [Appendix B](#).

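### SAP Appendix B gives BMD loss and bone fractures the same single search, so there is no separate fracture total; the hypoestrogenic row's exclusion of hot flashes has no terms behind it

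*SAP*

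**What the plan says.** SAP Appendix B opens with its purpose: "Adverse Events of Special Interest (AESI) will be identified using the following search criteria". Each row of its table pairs an item of safety interest with a method of surveillance. The two bone rows read "Bone mineral density loss Osteoporosis/Osteopenia SMQ" and "Bone Fractures Osteoporosis/Osteopenia SMQ". Neither names a list of preferred terms or a narrow or broad scope.

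The hot flashes row lists only the company query (CMQ) for non-bone-related hypoestrogenic effects. The row labelled "Hypoestrogenic AEs (excluding hot flashes, BMD loss, and fractures") lists the same query and nothing else.

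SAP 9.2.6 says "Adverse events of special interest will be summarized by SOC and PT". It bases the categories on standardized or company queries or on adjudication results, and sends the reader to Appendix B for the search detail. It does not say which items are adjudicated, or how.

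The protocol keeps these concepts apart. Section 6.1.1.3 states "AESIs include, but are not limited to rash/hypersensitivity, fracture, neuro-psychiatric (depression, mood swings, etc.) and vasomotor symptoms (hot flush, night sweats"). Section 6.1.4 lists bone fracture and clinically significant BMD loss as separate events to be collected in follow-up. Section 5.3.1.1 adds that a BMD decrease "that results in discontinuation from the study should be reported as an adverse event (Section 6.1.1").

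**The concern.** Four rows that are meant to be distinct rest on two searches. If the search defines the category, two rows with one search cannot give two answers.

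The bone pair matters more. Bone safety is a stated objective of this 48-month add-back trial. The SAP's bone section, 9.5.2, is confined to DXA measurements, so fractures are summarised only through the adverse event tables. The special-interest row is the only place where the plan provides a fracture total by arm. A reader of that row would take it as the number of women with a fracture.

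The hypoestrogenic pair has a milder form of the same fault. The label promises a total without hot flashes, but the plan does not say which terms to remove.

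**Working it through.** No sample-size or power figure bears on this. The check is a comparison of the Appendix B rows, followed by a check of what each shared search can return.

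**Step 1. Count the rows and searches.** Appendix B has 15 items. Grouped by identical search they give 13 distinct searches, so 15 − 13 = 2 rows duplicate another row's search. The only shared searches are the two pairs named above; the other 11 items each have their own.

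**Step 2. The bone pair.** Let O be the set of events returned by the Osteoporosis/Osteopenia SMQ.

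- BMD loss row, as written: O.
- Bone fractures row, as written: O.

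The rows therefore show the same events and the same number of women in every arm. This holds whatever the SMQ contains.

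Let F be the fracture events and B the BMD-loss events. The two rows would both be right only if O = F and O = B. F and B are different kinds of event, so O cannot equal both unless neither kind occurs. Otherwise at least one row fails to measure its label. Which row, and in which direction, depends on the SMQ contents, which the documents do not give.

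**Step 3. The hypoestrogenic pair.** Let C be the events returned by the company query and H the hot-flush events, whose terms are not listed.

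| Reading of the second row | Hot flashes row | Hypoestrogenic row |
|---|---|---|
| Search applied, label ignored | C | C (identical) |
| Label applied, hot flashes as Appendix B defines them | C | C minus C (empty) |
| Label applied, hot-flush terms chosen by the programmer | C | C minus H (H not specified) |

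The text permits all three. On every reading the hot flashes row, taken as written, is the whole query and not hot flushes alone.

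**Step 4. What the other planned output recovers.**

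- SAP 9.2.6 and 9.2.3 tabulate by system organ class and preferred term, so individual fracture, BMD and hot-flush terms are visible. A subject total is not recoverable by adding those rows, because a woman with two different terms is counted in each.
- SAP 9.2.7 summarises hot flushes and night sweats by severity and time to first onset. It gives no total for the other hypoestrogenic events.
- SAP 9.5.2 analyses BMD from DXA, so the bone-density question does not depend on the adverse event search.
- The any-special-interest-event line in SAP 9.2.2 is a union over categories. Two rows sharing a search do not of themselves change it.

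**The case against.** The strongest case against is that this is an underspecified mapping in descriptive tables. No hypothesis test, endpoint or error control depends on it. The preferred-term tables already show each event type, hot flushes have their own section and BMD has its own analysis. SAP 9.2.6 also allows adjudication as another basis. All of this is true and limits the harm to category totals. The adjudication route does not rescue the bone rows, since no item, process or criterion is named and Appendix B assigns them a query only.

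Two stronger readings are tempting, and the documents do not support them.

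- **All four rows collapse to two identical counts.** This follows for the bone pair. For the hypoestrogenic pair it requires ignoring the exclusion in the row's own label. The plan does specify a total without hot flashes; what is missing is the list of terms that would produce it.
- **The fracture row will be inflated by DXA findings.** Protocol 5.3.1.1 does require a BMD decrease leading to discontinuation to be reported as an adverse event. It does not say how that event is coded, and the SMQ contents are not given. Such events may enter the fracture row. Equally, if the SMQ held no fracture terms, the fault would be missed fractures. Any multiple put on the error would rest on invented counts.

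**Conclusion.** The point stands for the bone pair as a rule that gives a wrong result: one search defines two categories that the plan means to separate, so their totals must agree and no separate fracture total exists. This rests only on the Appendix B wording and on SAP 9.2.6 pointing nowhere else for the search detail.

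For the hypoestrogenic pair, the hot flashes row as written is too broad for its label. The second row's count is undefined and cannot be reproduced from the plan.

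Four of 15 categories are affected, at the level of category totals only. Efficacy inference, the DXA analyses and the preferred-term tables are untouched. The numerical effect cannot be stated, because neither the query contents nor any event counts are in the documents. The change is worth making because fracture and hypoestrogenic events are safety outcomes that readers of this trial will look for.

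**What to change.** Amend SAP Appendix B before the next database lock so that the two rows in each pair cannot overlap:

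1. **Bone fractures:** a pre-specified list of fracture preferred terms, whether or not they fall within the SMQ.
2. **BMD loss:** the Osteoporosis/Osteopenia SMQ terms that are not on the fracture list.
3. **Hot flashes:** named hot-flush preferred terms, stating whether night sweats are included. SAP 9.2.7 reports the two both separately and combined, and Appendix B mentions hot flashes only, so this is a choice to state and not one to assume.
4. **Other hypoestrogenic events:** the company query minus the terms in item 3.

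If any of these items is to be adjudicated, SAP 9.2.6 should name it.

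The cost is appendix wording and four term lists, with no new data and no change to study conduct. Drawing up the fracture list will also show whether the SMQ covers all fracture terms, which the present text leaves unknown. The small downside is that totals may differ from tables already run with the unsplit searches. The report should note any such difference.
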